#### 4.8.2 Secondary variables

Skin blood flow (LDF):

 $\Delta$  Depth: post-ischemic blood flow (depth) – pre-ischemic blood flow (depth)  $\Delta$  Shallow: post-ischemic blood flow (shallow) – pre-ischemic blood flow (shallow)

#### 5 Efficacy Endpoints

#### 5.1 Primary endpoint

Comparison of treatment groups for ΔFBF at week 20

Additional primary variable for extension period:

Comparison of treatment groups for pulse wave velocity at week 52

#### 5.2 Secondary endpoints

- Comparisons of groups and changes from baseline per treatment group for the following variables:
  - o PWV at week 52
  - o Maximal difference between baseline and post-ischemic skin blood flow FBF
  - Change of area under the FBF curve over 10 cycles of venous congestion (compared to baseline/day 0) at week 20 and EoT extension
  - Index of augmentation at weeks 20 and 52
  - o pulse wave velocity at 20 weeks and EoT Extension compared to baseline
  - change of maximal postischemic forearm blood flow during reactive hyperaemia after 5 min of forearm ischemia (FBF max. ml/100ml) at EOT after 52 weeks (EOT Extension)
  - o laboratory parameters (see above) at weeks 20 and 52

#### 6 Statistical Methods

#### 6.1 Data Handling

Concentrations below the lower limit of quantification will be set to zero by laboratory. In case a set of continuous data contains zeros, an analysis in log scale (as described in 6.3) will be omitted.

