#### 6.3 Hypothesis Testing

Unless otherwise specified all hypotheses will be tested at a 5% level of significance against two-sided alternative hypotheses.

Continuous variables will be analyzed by the following test procedures:

First of all the assumption of normally distributed data will be checked with Shapiro-Wilk test by treatment group. If the hypothesis of normally distributed data cannot be rejected for both treatment groups treatments will be compared by an ANCOVA procedure which includes "treatment" as the main factor and "baseline value" as covariate. T-Tests for independent samples will be used to compare groups at baseline.

In the event that the normality assumption is not warranted, data will be log-transformed and normality assumption of the transformed data will be checked by Shapiro-Wilk test. In case of non-rejection of the hypothesis of normally distributed data for both treatment groups, ANCOVA procedure and t-tests as described above will be performed on the basis of log-transformed data.

Point estimates and 95% CI of the difference in (adjusted) mean change from baseline will be provided if data are evaluated on basis of an ANCOVA procedure.

Otherwise Mann-Whitney's-U test on the basis of original data will be applied for comparison of groups at baseline. Mann-Whitney's-U test on the basis of intra-individual differences to baseline will be applied for treatment comparison per visits after baseline. Wilcoxon's signed rank test will be applied to evaluate changes from baseline per treatment group.

Categorical variables with 2 categories will be analyzed using Fisher's exact test (with Yates correction) to compare proportions between treatment groups. Variables with more than 2 categories will be compared by Pearson's Chi-square test. Additionally for each category, the proportions of treatment groups are compared using an (asymptotic) z test. Significant differences in proportions will be flagged, p-values for the z-test will not be shown.

Missing values will not be imputed.

If necessary, modifications of this general procedure will be described in the following sections of chapter 6.

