#### 6.11.2 Analysis of Secondary Endpoints

All secondary endpoints will be analyzed according to the procedure for continuous variables. Correlations (original data and changes from baseline) might be calculated.

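### One laboratory value below the quantification limit cancels the log-scale analysis of a skewed secondary biomarker and sends it to a rank test on raw change, without baseline covariate or planned estimate

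*SAP*

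**What the plan says.** SAP 6.1 (Data Handling) contains two linked rules. The first is: "Concentrations below the lower limit of quantification will be set to zero by laboratory". The second is: "In case a set of continuous data contains zeros, an analysis in log scale (as described in 6.3) will be omitted". The SAP does not say whether a set means a marker, a visit or an arm, and it names no number or share of zeros below which the rule does not apply.

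SAP 6.3 (Hypothesis Testing) fixes the order of analysis for continuous variables:

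- The gate: "First of all the assumption of normally distributed data will be checked with Shapiro-Wilk test by treatment group". If both arms pass on the raw scale, a baseline-adjusted ANCOVA is used.
- If not, the data are logged and tested again. If both arms pass, "ANCOVA procedure and t-tests as described above will be performed on the basis of log-transformed data".
- If not, "Mann-Whitney's-U test on the basis of intra-individual differences to baseline will be applied for treatment comparison per visits after baseline".
- Point estimates and 95% confidence intervals "will be provided if data are evaluated on basis of an ANCOVA procedure". None is specified for the rank branch.

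SAP 6.11.2 applies this sequence without modification: "All secondary endpoints will be analyzed according to the procedure for continuous variables". SAP 5.2 counts the laboratory parameters at weeks 20 and 52 among these endpoints. The primary forearm blood flow (FBF) endpoint has a different fallback in SAP 6.11.1, an ANCOVA on Blom-transformed ranks.

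**The concern.** A concentration below LLOQ is low, not absent. Zero is the most extreme value that could be entered. It pulls means and changes down further than any value between zero and the limit would, and it makes the logarithm undefined. The SAP thus creates the obstacle itself and then uses it as the reason to drop the log analysis.

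Inflammation, endothelial, coagulation and cardiovascular markers are the kind of variable for which the log step in SAP 6.3 exists. For a right-skewed marker the raw-scale gate will almost always fail. Once the log step is barred, only the Mann-Whitney branch is left. One unquantifiable sample can therefore remove the baseline covariate, the effect estimate and the interval together. The anti-inflammatory question is named in the trial title, so these results will be read closely even though they are secondary. If visits count as separate sets, two visits of one marker could also be analysed on different scales.

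**Working it through.** **Inputs from the documents.** SAP 2.4 gives 188 randomised and 141 evaluable at week 20, and 66 evaluable at week 52. Secondary tests are two-sided at 5% (SAP 6.3).

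**Inputs that are assumed.** The documents give no LLOQ, share below LLOQ, log-scale SD, baseline correlation or biomarker power. These are varied below. Markers are taken as log-normal, and the Shapiro-Wilk gate is applied to follow-up values.

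**1. The plan's own figure.** The FBF sample size gives the number per arm. With difference 1.2, SD 2.4, one-sided 5% and 90% power, the normal formula is 2 × (1.645 + 1.282)² × (2.4/1.2)² = 68.5, so 69 per arm. The t-test version needs 70. Then 70/0.75 = 93.3, so 94 per arm and 188 in total; 188 × 0.75 = 141. The plan's figure is reproduced, with about 70 evaluable per arm.

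**2. How easily the rule is triggered.** If a share q of samples is below LLOQ and samples are treated as independent, P(at least one zero) = 1 − (1 − q)^m, with m = 141 for one visit and m = 282 for baseline plus week 20.

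| q | one visit | two visits |
|---|---|---|
| 0.2% | 25% | 43% |
| 0.5% | 51% | 76% |
| 1% | 76% | 94% |
| 2% | 94% | 99.7% |

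Correlation between a patient's two samples would lower the two-visit column somewhat.

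**3. Power, main scenario.** 25% reduction, log-SD 0.8, baseline correlation 0.6, 70 per arm. Closed-form check for log-ANCOVA without non-detects: residual SD 0.8 × √(1 − 0.6²) = 0.64; SE 0.64 × √(2/70) = 0.108; −ln 0.75 = 0.288; 0.288/0.108 = 2.66; power ≈ Φ(2.66 − 1.96) = 76%. Simulated power:

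| Below LLOQ | Planned rule | LLOQ/2, gate kept | LLOQ/2, log-ANCOVA without gate | Blom-rank ANCOVA, zeros left in |
|---|---|---|---|---|
| 1% | 54% | 71% | 75% | 74% |
| 5% | 55% | 61% | 73% | 73% |
| 15% | 52% | 50% | 70% | 70% |

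Repeat runs of 1,500 to 2,000 simulated trials agree to within about 4 points, except that one put the rank ANCOVA at 68–70%. At 1,500 trials the Monte Carlo standard error is √(0.55 × 0.45/1500) = 1.3 points.

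The gain from LLOQ/2 with the gate kept is 71 − 54 = 17 points at 1%, 61 − 55 = 6 at 5%, and none at 15%. The substituted values form a spike in the lower tail, so the logged data fail Shapiro-Wilk. In one run they passed in 36% of trials at 5% and never at 15%.

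**4. Power over a wider grid.** Exactly one value below LLOQ, log-SD 0.5 to 1.0, correlation 0.3 to 0.7, effect set for 80% power with log-ANCOVA:

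- 70 per arm: 45–64% under the planned rule, 78–81% with ungated log-ANCOVA on LLOQ/2, 73–78% with LLOQ/2 and the gate kept. Every simulated marker went to Mann-Whitney under the planned rule.
- 33 per arm (week 52): 44–60% under the planned rule, 75–80% with ungated log-ANCOVA.
- Rank ANCOVA at 70 per arm with 1% or 5% zeros: 75–80%.

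**5. Where the loss is small.** At correlation 0.85 and log-SD 0.5 it is 6–9 points. At correlation 0.85 and log-SD 0.3 it is about 5 points at 1% below LLOQ, and Mann-Whitney is slightly better at 5%.

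**6. Type I error.** With no treatment effect the planned rule rejects in 5.0–5.2% of trials.

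**The case against.** The strongest reply is that the rule is pre-specified, keeps its error rate, and touches only secondary markers in a trial that Protocol 9.1.5 calls explorative. Once zeros are in the data, omitting logs is a mathematical necessity. All of this is true. It limits the harm to power and estimation, but it does not justify entering the zeros.

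A second reply is that every biomarker input is assumed. This stands for the numbers. The mechanism rests on the text alone. Protocol 4.11.1 requires raised hsCRP and/or PAI-1 at or within six months before screening, so non-detects are less likely for at least one of those two markers in each patient. No such criterion covers the other markers.

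Some stronger readings are tempting but not supported:

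- **Substituting LLOQ/2 recovers about 20 points by itself.** It does not. With the SAP 6.3 gate in place, most of the gain is gone at 5% below LLOQ and all of it at 15%.
- **The fallback ignores baseline.** It uses change from baseline; only the covariate is missing.
- **One zero always costs the whole marker its log analysis.** The set is undefined. If it means one visit, the chance at 1% is 76%, not 94%. Raw data that pass Shapiro-Wilk also still get ANCOVA, although that is rare for skewed markers at 70 per arm.
- **The primary endpoints are exposed.** Neither FBF nor pulse wave velocity is a concentration, and FBF has its own fallback.

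**Conclusion.** The concern holds for secondary laboratory concentrations. A single non-detect bars the log-scale step, and a skewed marker then gets a rank test on raw change with no covariate and no planned estimate or interval. In the main scenario the cost is 18 to 21 points of power (75 − 54, 73 − 55 and 70 − 52 at 1, 5 and 15% below LLOQ). Over the wider grid with one non-detect at 70 per arm it is 14 to 36 points. It falls to about 5–9 points for mildly skewed markers with high baseline correlation, and can vanish.

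The mechanism is certain from SAP 6.1, 6.3 and 6.11.2. The sizes depend on assumed log-normality, SDs, correlations and non-detect rates. At 5% below LLOQ and above, most or all of the loss comes from the normality gate and the choice of fallback, so changing the substituted value alone is not enough. A reader might infer that false positive findings become more likely; the simulations under no effect show no sign of that.

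**What to change.** Change SAP 6.1, 6.3 and 6.11.2 before the data are analysed:

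1. Have the laboratory report non-detects as below the limit, together with the limit, instead of zero.
2. Delete the rule that omits the log-scale analysis when zeros are present.
3. For laboratory concentrations, pre-specify a baseline-adjusted ANCOVA on the log scale with LLOQ/2 for non-detects, not conditional on Shapiro-Wilk. Report the estimate and 95% confidence interval for every marker analysed this way.
4. Where the share below LLOQ is high (for example above 25%), or as the general fallback in place of Mann-Whitney on change, use the Blom-rank ANCOVA already planned for FBF in SAP 6.11.1.
5. Report the number below LLOQ by marker, arm and visit.

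The cost is SAP wording, a laboratory export setting and slightly more analysis work. The downside is that LLOQ/2 is a conventional value, not a measured one. The counts in step 5 let a reader judge how much it matters. This is a cheap improvement.

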#### 6.2 Descriptive or summary statistics

All continuous variables will be summarized by treatment group using the following statistics: n (non-missing sample size), number of missing values (Missing), arithmetic mean (Mean), standard deviation, (STD), median (Median), maximum (Max) and minimum (Min).

Tables for original (untransformed) data will be provided as well as tables for differences from baseline by visit. Boxplots will be presented for illustration.

For nominal or categorical data, frequencies and percentages (based on the non-missing sample size) will be tabulated for each category.

#### 6.3 Hypothesis Testing

Unless otherwise specified all hypotheses will be tested at a 5% level of significance against two-sided alternative hypotheses.

Continuous variables will be analyzed by the following test procedures:

First of all the assumption of normally distributed data will be checked with Shapiro-Wilk test by treatment group. If the hypothesis of normally distributed data cannot be rejected for both treatment groups treatments will be compared by an ANCOVA procedure which includes "treatment" as the main factor and "baseline value" as covariate. T-Tests for independent samples will be used to compare groups at baseline.

In the event that the normality assumption is not warranted, data will be log-transformed and normality assumption of the transformed data will be checked by Shapiro-Wilk test. In case of non-rejection of the hypothesis of normally distributed data for both treatment groups, ANCOVA procedure and t-tests as described above will be performed on the basis of log-transformed data.

Point estimates and 95% CI of the difference in (adjusted) mean change from baseline will be provided if data are evaluated on basis of an ANCOVA procedure.

Otherwise Mann-Whitney's-U test on the basis of original data will be applied for comparison of groups at baseline. Mann-Whitney's-U test on the basis of intra-individual differences to baseline will be applied for treatment comparison per visits after baseline. Wilcoxon's signed rank test will be applied to evaluate changes from baseline per treatment group.

Categorical variables with 2 categories will be analyzed using Fisher's exact test (with Yates correction) to compare proportions between treatment groups. Variables with more than 2 categories will be compared by Pearson's Chi-square test. Additionally for each category, the proportions of treatment groups are compared using an (asymptotic) z test. Significant differences in proportions will be flagged, p-values for the z-test will not be shown.

Missing values will not be imputed.

If necessary, modifications of this general procedure will be described in the following sections of chapter 6.

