# Pulse wave velocity and arterial stiffness:

	Measurements will be performed using the Mobil-O-Graph device (IEM Inc., Stolberg, Germany). This device allows the non-invasive oscillometric analysis of blood pressure and pulse wave over 24 hours. Based on pulse wave analysis we calculate the aortic augmentation index as marker of arterial stiffness and pulse wave velocity. The Mobil-O-Graph device has been validated against gold standard procedures such as applanation tonometry (SphygmoCor, AtCor Inc.).	
Measurement of	Assessment of platelet activation and mitogenic potential	
results	Platelet activation will be assessed by measuring platelet derived microparticles (PMP) by separating platelet poor plasma from platelet rich plasma. Subsequently, analysis of platelet microparticles and their mitogenic potential will be performed after sample thawing. PMP will be measured after staining with anti-GP1b antibodies by fluorescence-activated cell sorting (FACS). In addition, magnetic beads linked with anti-GP1 b antibodies will be used to extract PMP from platelet poor plasma. Extracted PMP will then be added to human vascular endothelial cells (HUVECS) and migration (Boyden chamber) as well as proliferation (BrdU) of HUVECs will be assessed with and without PMP with samples from patients undergoing platelet inhibition or rivaroxaban treatment. Platelet rich plasma will be used to measure platelet activation by cGMP dependent phosphorylation of vasodilator-stimulated phosphoprotein (VASP) at Ser-157 which will be detected by flow cytometry.	
Statistical methods	Efficacy: The statistical analysis will be done in the intention to treat and per protocol set. The primary parameter will be the maximum FBF at 20 weeks (assessed with venous occlusion plethysmography after forearm ischemia) controlling for baseline FBF and the Pulse Wave Velocity (PWV) at EOT (extended treatment period after 52 weeks) assessed with a sphygmograph (Mobilograph®, IEM) using an analysis of covariance (ANCOVA). Independent t-test will be used to test the parameters between the groups at the time point as well as the change between baseline and 20 weeks of treatment. Additionally, measurements will also be compared to an extended treatment up to 52 weeks (EOT Extension). Safety: Analysis of bleeding events and safety parameters is required.	

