#### 6.11.1 Analysis of Primary Endpoint

Primary study endpoint:

The hypothesis H0 is tested against the **one-sided** alternative hypothesis H1

```
H0: \mu_{\Delta FBF,Riva, week 20} \leq \mu_{\Delta FBF, ASS, week 20} vs. H1: \mu_{\Delta FBF, Riva, week 20} > \mu_{\Delta FBF, ASS, week 20}
```

by test procedures for continuous data. In case of non-rejection of the normality hypothesis an ANCOVA procedure for repeated measurements will be applied. For repeated measurements per subject an AR(1)-covariance-structure will be specified. Otherwise ANCOVA for repeated measurements will be based on (Blom-transformed) rank data.

Primary endpoint for the extension period:

The hypotheses

```
H0: \mu_{PWV, Riva, week 52} = \mu_{PWV, ASS, week 52} VS. H1: \mu_{PWV, Riva, week 52} \neq \mu_{PWV, ASS, week 52}
```

will be tested by procedure for continuous data.

Age, gender and duration of diabetes might represent confounding factors and could thus be included as covariates in the statistical model. Models incorporating different combinations of covariates are compared with respect to their model fit. The best fitting model according to the QIC (Quasi-Likelihood information) -criterion will be finally chosen for analysis.

Correction procedures for multiple comparisons are not necessary due to the fact that both primary endpoints consist in single comparisons addressing different variables.

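### A by-arm Shapiro-Wilk test chooses the scale of both primary analyses, so an adjusted difference with CI in ml/100ml (FBF) or m/s (PWV) is not guaranteed

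*SAP*

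**What the plan says.** **General rule (SAP 6.3).** "First of all the assumption of normally distributed data will be checked with Shapiro-Wilk test by treatment group". If neither arm rejects, the arms are compared by ANCOVA with the baseline value as covariate. If either rejects, there is a second step: "In the event that the normality assumption is not warranted, data will be log-transformed", normality is tested again, and ANCOVA is run on the log scale if both arms pass. Only if that also fails does a Mann-Whitney test "on the basis of intra-individual differences to baseline will be applied for treatment comparison per visits after baseline". An adjusted estimate is tied to the branch: "Point estimates and 95% CI of the difference in (adjusted) mean change from baseline will be provided if data are evaluated" by ANCOVA. SAP 6.1 drops the log step when the data contain zeros.

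**Week-20 FBF (SAP 6.11.1).** "In case of non-rejection of the normality hypothesis an ANCOVA procedure for repeated measurements will be applied". "Otherwise ANCOVA for repeated measurements will be based on (Blom-transformed) rank data". This section does not mention the log step. Since SAP 6.3 lets later sections of chapter 6 modify the general procedure, it is unclear whether the log step comes before the ranks.

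**Week-52 PWV (SAP 6.11.1).** It is tested by the general procedure for continuous data, so the SAP 6.3 sequence applies.

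**Protocol.** The synopsis plans ANCOVA for both primary variables, with FBF adjusted for baseline. Section 9.2 plans an independent-samples t-test. Neither has a normality-dependent switch.

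**The concern.** The hypotheses in SAP 2.4 and 6.11.1 are about means, and the sample sizes rest on 1.2 ml/100ml and 0.7 m/s. A reader of the trial report will want the adjusted difference between arms in those units, with its interval. Under the SAP, whether that result exists depends on a significance test applied to the outcome after the data are in.

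The test also looks at the wrong quantity. ANCOVA needs roughly normal residuals, not raw values that are normal within each arm, and with samples of this size it tolerates moderate skewness. Shapiro-Wilk will reject for skewness that does ANCOVA no harm. After a switch the question changes: a difference in normal scores or a ratio on the log scale cannot be set against 1.2 ml/100ml or 0.7 m/s, and a Mann-Whitney test on change scores carries no adjusted estimate.

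**Working it through.** **Inputs**
- FBF: difference 1.2, SD 2.4 ml/100ml, one-sided 5%, power 90%, dropout 25%, 188 randomised, 141 evaluable (Protocol 9.1.8, SAP 2.4).
- PWV: difference 0.7, SD 1.0 m/s, 5%, power 80%, 66 evaluable (same sections).
- Pre-test level: none is stated for Shapiro-Wilk. I assume 5% from the general rule, "Unless otherwise specified all hypotheses will be tested at a 5% level of significance against two-sided alternative hypotheses".
- Skewness and baseline correlation: not in the documents, so assumed and varied or stated.

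**1. The plan's numbers per arm.** FBF: n = 2(1.645 + 1.282)² × (2.4/1.2)² = 68.5 per arm. The t-based solution is 69.2, so 70; 70/0.75 = 93.3, so 94 per arm and 188 in total, as stated. Evaluable: 188 × 0.75 = 141, about 70 per arm. PWV: the t-based two-sided solution is 33.02 per arm, which matches 66 evaluable. The check below therefore uses 70 and 33 per arm.

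**2. How often the first check fails with exactly normal data.** Both arms must pass, so 1 − 0.95² = 9.75%. SAP 4.8.1 defines 8 post-ischemic values per visit, and the mock table in SAP 7.6.1 has a normality p-value column for them; the SAP does not say which value decides the branch. If all 8 were tested in both arms, the figure is 1 − 0.95¹⁶ = 56% under independence. This is an upper end, because values within a patient are correlated.

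**3. How often it fails with skewed data.** Simulated trials, gamma-distributed data, Shapiro-Wilk p < 0.05 in at least one arm (3,000 to 4,000 trials per setting, rounded):

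| Skewness | 70 per arm (FBF) | 33 per arm (PWV) |
|---|---|---|
| 0 | 10% | 10% |
| 0.3 | 25% | 17% |
| 0.5 | 50% | 29% |
| 0.7 | 78% | 47% |
| 1.0 | 97% | 73% |

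**4. Where the failing trials go.**
- FBF, log step not applied: all go to Blom ranks. There, a true difference of 1.2 ml/100ml appears as about 0.50 to 0.60 normal-score units (skewness 0.5 to 1.5).
- FBF, log step applied: ranks are reached in about 8%, 52% and 84% of trials at skewness 0.5, 1.0 and 1.5 (gamma data). The other failing trials give a log-scale result, also not in ml/100ml.
- PWV: Mann-Whitney is reached in about 5%, 8% and 19% of trials at skewness 0.5, 0.7 and 1.0 (about 9% to 34% at 1.0 if the coefficient of variation is set to 0.3 or 0.15). The other failing trials give a baseline-adjusted log-scale ANCOVA.

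**5. Error rate and power of the two FBF strategies.** 2,000 trials per setting, 70 per arm, one-sided 5%, SD 2.4, one outcome value per patient, assumed baseline correlation 0.5, no log step:

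| Skewness | Type I error: fixed ANCOVA | Type I error: branched | Power: fixed ANCOVA | Power: branched |
|---|---|---|---|---|
| 0.5 | 4.4% | 5.0% | 95.1% | 95.7% |
| 1.0 | 5.3% | 5.3% | 94.6% | 98.0% |
| 1.5 | 5.2% | 5.2% | 95.4% | 99.7% |

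The fixed analysis returned a mean estimate of 1.19 to 1.20 ml/100ml. Monte Carlo error for a 5% rate is √(0.05 × 0.95/2000) = 0.5 percentage points, so neither strategy departs from its nominal level. At 33 per arm, fixed ANCOVA also held its level at about 5% with unbiased estimates for skewness 0.5 to 1.5.

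**The case against.** The strongest defence is that the branching is written down in advance, keeps type I error near 5% and, if anything, gains power with skewed data. The protocol also calls the trial exploratory (9.1.5) and a pilot (2.1). The points on error rate and power stand. The point on prespecification stands only in part: the SAP does not say which FBF values are tested or whether the log step applies to FBF.

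Four stronger readings are tempting, and the documents do not support them:
- **That the two-stage procedure distorts the error rate.** A reader might infer this from the pre-test, but step 5 shows no sign of it for FBF, and nothing in the documents establishes it.
- **That PWV and all secondary endpoints lose baseline adjustment once normality is rejected.** SAP 6.3 puts a log-scale ANCOVA with the baseline covariate in between, and its promise of estimates and intervals covers that ANCOVA. Adjustment can be lost, but only if the second check also fails or zeros rule out the log.
- **That the loss equals the usual variance ratio of change scores to ANCOVA, 2/(1+r), with r the baseline correlation.** That ratio compares two analyses of means. It does not describe a rank test, and the Blom branch for FBF is still an ANCOVA.
- **That nothing remains on the original scale.** SAP 6.2 requires means and SDs of the original data and of the differences from baseline on every branch. What is missing is the adjusted between-arm difference with its CI.

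**Conclusion.** The point holds as one about the estimand and its interpretation. An outcome-data test decides whether the two primary comparisons are reported in the units in which the hypotheses and sample sizes are stated. The switch occurs in about 1 trial in 10 with exactly normal data. At skewness 0.5 it occurs in about half of trials for FBF and 29% for PWV; at skewness 1.0, in 97% and 73%.

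These are ranges, not forecasts. They assume a 5% pre-test, gamma-shaped data and one tested value per patient, and the documents give no skewness for either variable. The error-rate and power comparison was made for FBF without the AR(1) repeated-measures model. Sample size is unaffected. The change is worth making as a cheap improvement; the documents do not show that the planned tests are invalid.

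**What to change.** In SAP 6.3 and 6.11.1:
- Make baseline-adjusted ANCOVA on the original scale the primary analysis of week-20 FBF and week-52 PWV, whatever Shapiro-Wilk shows.
- Always report the adjusted between-arm difference with its CI, in ml/100ml and m/s.
- Check residuals graphically instead of testing raw values by arm.
- Keep Blom-rank ANCOVA (FBF) and the log-scale or rank analysis (PWV) as named sensitivity analyses.
- For skewed biomarkers, fix the log scale in advance, variable by variable.

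The cost is SAP wording only; 188 patients and the extension of 80 stay as they are. The downside is reliance on large-sample robustness, more so for PWV at about 33 per arm, and possibly slightly less power than ranks if the data are strongly skewed (about 95% against 98.0% to 99.7% at skewness 1.0 to 1.5 in the FBF simulation). The sensitivity analyses cover that case.
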